13.5 Analysis of Primary Endpoints

Please refer to section 13.1.

13.6 Analysis of Secondary Endpoints

The analysis of secondary endpoints will be primarily descriptive, including rate of PR after 15 cycles of therapy, rate of CR/CRi after 15 cycles of therapy, rate of best overall response, best rate of CR/CRi, best rate of peripheral blood and bone marrow MRD, progression free survival (including 2-year and 3-year landmark rate), overall survival (including 2-year and 3-year landmark rate), rate of MRD negativity in the bone marrow at 8 and 24 cycles, rate of peripheral blood MRD-negativity at 8, 15, and 24 cycles, correlation between MRD-negativity in the peripheral blood and bone marrow, time to MRD-positive disease recurrence in the peripheral blood, time to clinical disease progression, rate of infusion related reactions, and rate of tumor lysis syndrome. A descriptive analysis of rates of therapy discontinuation after 15 cycles will be performed, with subjects grouped by reasons for discontinuation (e.g. achievement of MRDnegative CR, progressive disease, or intolerability). Rates of discontinuation of individual components of the regimen will also be included in this analysis. The Kaplan Meier method will be used to estimate the median progression-free survival time, progression-free survival, median overall survival time, and overall survival. Association between clinical response and established CLL prognostic factors (ZAP70, FISH cytogenetics, IGHV mutation status, TP53 mutation status) will be tested using Fisher's exact test. A similar descriptive analysis will be performed for laboratory correlative studies of BH3 profiling and genomic markers such as SF3B1, NOTCH1, and BCR/NFKB pathway somatic mutations. If feasible, association between clinical response and correlative endpoints will be explored. A descriptive safety analysis with attention to adverse events, adverse events of special interests, and serious adverse events will also be performed. We also plan to perform the above efficacy and safety analyses on cohort 1, cohort 2 plus the patients with TP53 aberrant disease in cohort 1, and in the entire group of cohort 1 plus cohort 2

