Long-term follow-up data from both chemoimmunotherapy trials and also early trials of novel agent monotherapy in CLL have demonstrated that patients with TP53-aberrant disease remain an unmet need. TP53 aberrations include deletions of chromosome 17p (detected by either karyotype or FISH) or mutations in TP53 itself. It has long been known that patients with TP53 aberrations have lower response rates and shorter responses to standard chemoimmunotherapy. For example, in the CLL8 trial that compared FC to FCR for the up-front treatment of CLL, the group of patient with either TP53 mutations or del(17p) had a PFS of approximately 12 months and an OS of approximately 40 months, shorter than any other genetically defined subgroup (Stilgenbauer et al., 2014). Regarding novel agents, the longest follow-up available is with ibrutinib (primarily in relapsed/refractory patients), and again this data suggests that while the overall response rates among those with and without del(17p) are similar, the presence of del(17p) clearly defines a subgroup of patients with a shorter duration of response to ibrutinib. After 5 years of follow-up on patients treated with ibrutinib monotherapy, a median PFS of only 26 months was seen in patients with del(17p), compared to a median PFS of 51 months for the overall group of relapsed/refractory patients. Furthermore, a multivariate analysis in this same population demonstrated that del(17p) was an independent risk factor for shorter PFS (S. O'Brien et al., 2018). In a study with shorter follow-up that examined the use of ibrutinib in the front-line setting outside of a clinical trial, patients with del(17p) again had an inferior PFS compared to those without del(17p) (Mato et al., 2018). These data support the conclusion that novel agent

monotherapy will be unable to reliably achieve durable responses in patients with *TP53*-aberrant disease and provide rationale for expanding this study to include more patients from this high-risk population. In addition to the unmet need, further justification for focusing our expansion cohort on these high risk patients is that the quality of response in our initial 12 patients treated on study to date (including 3 patients with *TP53*-aberrant disease) did not differ based on *TP53* status. This provides preliminary evidence that the "AVO" triplet regimen may potentially be able to overcome the inherent resistance of this high risk form of CLL.

Summary

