3. PARTICIPANT SELECTION

3.1 Eligibility Criteria

Unless otherwise specified, laboratory tests required for eligibility must be completed within 2 weeks prior to start of protocol therapy. Baseline tumor measurements by CT or PET/CT scan must be performed within approximately 30 days of starting study treatment. Bone marrow biopsy within approximately 6 months prior to study treatment will be acceptable if there has not been significant anti-cancer therapy given since the test was performed.

Inclusion Criteria

Participants must meet the following criteria on screening examination to be eligible to participate in the study:

- Subjects must meet IWCLL 2018 guidelines for the diagnosis of CLL or SLL, or WHO 2017 guidelines for the diagnosis of B-prolymphocytic leukemia (B-PLL)
- In cohort 2, subjects must have *TP53*-aberrant disease defined as:
 - o Del(17p) detected by karyotype, FISH, or next-generation sequencing; OR
 - o TP53 mutation
- Participants must have measurable disease (lymphocytosis > 5,000 / μ l, or palpable or CT measurable lymphadenopathy \geq 1.5 cm, or bone marrow involvement \geq 30%).
- Subjects must not have received any prior systemic therapy for CLL or SLL due to
 previously meeting IWCLL 2018 guidelines and must currently have an indication for
 treatment as defined by the IWCLL 2018 guidelines, or must not have received therapy
 for B-PLL and must currently have an indication for treatment:
 - Massive or progressive or symptomatic splenomegaly; OR
 - o Massive lymph nodes, nodal clusters, or progressive lymphadenopathy; OR
 - Significant fatigue (i.e. ECOG PS 2 or worse; cannot work or unable to perform usual activities); OR
 - Fever ≥ 100.5 °F for 2 or more weeks without evidence of infection; OR
 - Night sweats for ≥ 1 months without evidence of infection; OR
 - Presence of weight loss $\geq 10\%$ over the preceding 6 months; OR
 - Progressive lymphocytosis with an increase of \geq 50% over a 2-month period or lymphocyte doubling time of less than 6 months; OR
 - Evidence of progressive marrow failure as manifested by the development of or worsening of anemia and/or thrombocytopenia.
 - Autoimmune anemia and/or thrombocytopenia that is poorly responsive to corticosteroids and another standard therapy such as rituximab
 - Symptomatic or functional extranodal involvement; OR
- Age greater than or equal to 18 years. Because CLL is extremely rare in persons <18 years of age, children are excluded from this study.

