13.2 Sample Size, Accrual Rate and Study Duration

This is a one-stage study to determine the MRD-negative CR/CRi rate in the bone marrow after 15 cycles of AVO combination therapy. In a previous study of venetoclax plus rituximab in the relapsed/refractory population, the CR/CRi rate was 51%, and 80% of these responses were bone-marrow MRD-negative, for an MRD-negative CR/CRi rate of 41% (Seymour et al., 2017). Furthermore, 21 out of 25 CRs in this study occurred after 18 months of therapy, thus we will assume that ~80% of all marrow MRD-negative CRs will have occurred after 15 months of therapy here, leading to an expected marrow MRD-negative CR/CRi rate of 33%. Of note, this study was done in a relapsed/refractory population. Given that the depth of response is likely to be greater in the frontline setting, we are using an MRD-negative CR/CRi rate of 40% as the null hypothesis. With the addition of acalabrutinib, we hypothesize that the MRD-negative CR/CRi rate will be 60% or higher (alternative hypothesis). Initially, we planned to enroll 37 patients, and assuming approximately 1 screening failure this meant that 36 patients would be evaluable for the primary endpoint. This cohort has now completed enrollment and is referred to as cohort 1. We will now expand the study to include a second cohort of 35 patients with high-risk disease, defined as 17p deletion and/or TP53 mutation (cohort 2). In cohort 2, we will have 80% power and one-sided type I error of 0.07 for an exact one-sample binomial test comparing an expected 55% response rate to the assumed 35% response rate for standard-of-care treatment in this high risk group. A patient will be considered unevaluable for response and replaced if the patient decides to withdraw from the study prior to the administration of the first dose of study drug. Based on the accrual rate of the study to date of 3 patients per month, we anticipate that accrual

of this study will complete within approximately 12 months from activation of cohort 2. Up to an additional 15 months of follow-up will be required on the last participant accrued to observe participant response after the 15th cycle of protocol therapy, for a total study duration of approximately 2.5 years. Evaluation of secondary endpoints, such as 3 year overall survival, will take up to three years after enrollment of the final subject.

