13.3 Stratification Factors

There will be no stratification of patients on this study.

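### The combined cohort 1 plus cohort 2 analyses mix in an all-TP53-aberrant cohort, and the pooled marker tests are not stratified by TP53 status

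*Combined protocol and SAP*

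**What the plan says.** Section 13.6 plans the secondary analyses, for efficacy as well as safety, in three sets. The first two are given as "on cohort 1, cohort 2 plus the patients with TP53 aberrant disease in cohort 1". The third pools everyone: "and in the entire group of cohort 1 plus cohort 2". The section describes these analyses as mainly descriptive. It uses Kaplan-Meier for PFS and OS, and states that the association between clinical response and ZAP70, FISH cytogenetics, IGHV and TP53 mutation status "will be tested using Fisher's exact test". It gives no adjustment for TP53 or cohort, no rule for interpreting the combined set, and no set made up only of non-aberrant patients.

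Cohort composition comes from two other places. Section 3.1: "In cohort 2, subjects must have *TP53*-aberrant disease defined as" a del(17p) or a TP53 mutation. Section 13.2: "We will now expand the study to include a second cohort of 35 patients with high-risk disease, defined as 17p deletion and/or TP53 mutation"; for cohort 1, "this meant that 36 patients would be evaluable for the primary endpoint".

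Section 13.3 adds: "There will be no stratification of patients on this study". That line is about stratifying patients, so it is only weak evidence on how the analyses are to be adjusted.

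**The concern.** Cohort 1 was not selected on TP53; cohort 2 is selected on nothing else. Putting them together gives a set in which the share of high-risk patients is fixed by how many were enrolled to cohort 2. If outcome differs by TP53 status, a single response rate or survival curve for that set would move with the size of cohort 2 even if the regimen's effect in each group stayed the same.

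The marker tests are the more practical worry. If unmutated IGHV or ZAP70 positivity is more common in TP53-aberrant patients, and those patients respond less often, an unstratified Fisher test in the combined set can show an association that does not exist within either TP53 group. Section 2.4 says the expansion is meant to make the secondary and subgroup analyses more robust, so these tests are likely to be read seriously.

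The pooled TP53 comparison has a related difficulty. Every non-aberrant patient comes from cohort 1. Most aberrant patients come from the later cohort, and Section 2.4 plans to open community sites with a different patient population.

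**Working it through.** **The plan's own figure.** No figure is stated for the combined set. The nearest is the cohort 2 design in Section 13.2: n = 35, 35% versus 55%, one-sided 0.07, 80% power. It reproduces. With success at 17 or more responses, the exact type I error is 0.068 and power is 0.825. The point below does not touch that design.

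**Inputs**
- Cohort 1: 36 evaluable. Cohort 2: 35, all TP53-aberrant (Sections 13.2 and 3.1). Combined: 71.
- TP53-aberrant count k in cohort 1: the final count is not given. Section 2.4 reports 3 of the first 12 (25%). Assumed range: k = 4 to 13.
- Response rates by TP53 status: not given. Section 13.2 hypothesises 60% for cohort 1 overall and 55% for cohort 2. Using 60% as the non-aberrant rate is an assumption, and 60%/35% is an assumed larger gap.

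**TP53-aberrant share of the combined set** = (35 + k)/71
- k = 4: 39/71 = 55% (cohort 1: 11%)
- k = 9: 44/71 = 62% (cohort 1: 25%)
- k = 13: 48/71 = 68% (cohort 1: 36%)

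**Shift in the response rate.** For non-aberrant rate a and aberrant rate b, cohort 1 expects [(36 − k)a + kb]/36 and the combined set expects [(36 − k)a + (35 + k)b]/71. With k = 9:
- 60%/55%: cohort 1 (27 × 0.60 + 9 × 0.55)/36 = 58.7%; combined (27 × 0.60 + 44 × 0.55)/71 = 56.9%; shift 1.8 points.
- 60%/35%: cohort 1 (27 × 0.60 + 9 × 0.35)/36 = 53.7%; combined (27 × 0.60 + 44 × 0.35)/71 = 44.5%; shift 9.2 points.
- Equal rates: shift 0.

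Over k = 4 to 13 the shift is about 2 points in the first case and 8 to 11 points in the second.

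**Fisher's test under no marker effect.** Simulated with 27 non-aberrant and 44 aberrant patients, and a marker with no effect on response within either TP53 group. Test two-sided at a nominal 5%. Rates and marker prevalences are written non-aberrant/aberrant; the prevalences are assumptions.

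| Response | Marker prevalence | Unstratified Fisher | Exact test stratified by TP53 status |
|---|---|---|---|
| 60%/55% | 50%/80% | about 4% | about 4% |
| 65%/40% | 55%/80% | 6.6% | 3.6% |
| 70%/35% | 50%/85% | 15.7% | about 3% |

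Where marker prevalence is the same in both TP53 groups, or response does not differ by TP53, the unstratified test rejects about 3% to 4% of the time. Excess false positives need both differences together.

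**The case against.** The plan already does much of what is needed. The same sentence of Section 13.6 lists cohort 1 alone and all TP53-aberrant patients, and both can be interpreted without the combined set. For binary endpoints, the non-aberrant counts follow by subtraction. The analyses are mainly descriptive, and no hypothesis or error rate attaches to the combined set. On the sponsor's own hypothesised rates the shift is about 2 points and Fisher's test stays below its nominal level. The only evidence from the trial itself points the same way: Section 2.4 reports that the "quality of response in our initial 12 patients treated on study to date" did not differ by TP53 status. All of this stands, and it limits the size and seriousness of the point. It does not remove it. Twelve early patients, three of them aberrant, cannot establish equal response, and Section 13.6 does plan to test the associations.

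Four stronger readings are tempting, and the documents do not support them.
- A reader might infer that pooled results reflect the enrolment mix instead of the regimen. They reflect both.
- A reader might infer that the all-aberrant set offers no TP53 contrast. The factor in Section 13.6 is TP53 mutation status, and eligibility also admits patients with del(17p) alone, so mutated versus del(17p)-only can be compared there.
- A reader might project a PFS distortion from the 26- and 51-month ibrutinib medians in Section 2.4. The 51 months is for the overall relapsed/refractory group, not patients without del(17p), and neither figure concerns this frontline triplet.
- A reader might extend the Fisher problem to PFS and OS. Section 13.6 specifies that test for clinical response only.

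**Conclusion.** The point holds as a modest, inexpensive improvement to the secondary analyses. By eligibility, the combined set will be far richer in TP53-aberrant disease than cohort 1, and the plan neither says how to read it nor stratifies the marker tests run in it.

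The practical effect ranges from none (response equal by TP53), through about 2 points on the response rate and no inflation of Fisher's test (60%/55%), to about 9 points (60%/35%). Null rejection reaches about 7% to 16% when response and marker prevalence both differ materially by TP53. The final TP53 count in cohort 1, the larger response gaps and the marker prevalences are assumptions, because the documents do not give them. The pooled TP53 comparison remains usable but is partly confounded with cohort, enrolment period and the added sites.

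**What to change.** In Section 13.6:
1. Label the combined set as supportive.
2. Report its rates and Kaplan-Meier estimates by TP53-aberrant status, adding the non-aberrant group explicitly.
3. In that set, replace the unstratified Fisher test of response against IGHV and ZAP70 with an exact test stratified by TP53-aberrant status.
4. For FISH, compare the categories other than del(17p) within TP53 strata, because del(17p) is part of the stratum definition.
5. Keep the pooled TP53 comparison, with a sentence stating its partial confounding with cohort, period and sites.

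The cost is a few lines of wording, a little more analysis of data already collected, and some loss of nominal power in the stratified tests.

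Two further steps are not recommended. Confining the TP53 association to cohort 1 would leave about 27 versus 9 patients: Fisher power for 60% versus 35% would be 19%, against 49% with 27 versus 44 in the combined set. Standardising an overall figure to cohort 1's TP53 share adds little, since cohort 1 is already reported alone.

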13.7 Reporting and Exclusions

Subjects who never start protocol therapy will be excluded from all analyses.

Evaluation of Toxicity

All participants who receive any amount of study therapy will be evaluable for toxicity from the time of their first treatment.

Evaluation of the Primary Efficacy Endpoint

All participants who receive at least one dose of at least one of the study drugs will be considered evaluable for the primary efficacy endpoint in an intent-to-treat analysis.

14. PUBLICATION PLAN

The results should be made public within approximately 24 months of reaching the end of the study. The end of the study is the time point at which the last data items are to be reported, or after the outcome data are sufficiently mature for analysis, as defined in the section on Sample Size, Accrual Rate and Study Duration. If a report is planned to be published in a peer-reviewed journal, then that initial release may be an abstract that meets the requirements of the International Committee of Medical Journal Editors. A full report of the outcomes should be made public no later than three (3) years after the end of the study.

APPENDIX A: PERFORMANCE STATUS CRITERIA

ECC	OG Performance Status Scale	Karnofsky Performance Scale		
Grade	Descriptions	Percent	Description	
0	Normal activity. Fully active, able to carry on all pre-disease	100	Normal, no complaints, no evidence of disease.	
U	performance without restriction.	90	Able to carry on normal activity; minor signs or symptoms of disease.	
1	Symptoms, but ambulatory. Restricted in physically strenuous activity, but ambulatory and able	80	Normal activity with effort; some signs or symptoms of disease.	
1	to carry out work of a light or sedentary nature (e.g., light housework, office work).	70	Cares for self, unable to carry on normal activity or to do active work.	
2	In bed <50% of the time. Ambulatory and capable of all self-care, but unable to carry out	60	Requires occasional assistance, but is able to care for most of his/her needs.	
	any work activities. Up and about more than 50% of waking hours.	50	Requires considerable assistance and frequent medical care.	
3	In bed >50% of the time. Capable of only limited self-care, confined	40	Disabled, requires special care and assistance.	
3	to bed or chair more than 50% of waking hours.	30	Severely disabled, hospitalization indicated. Death not imminent.	
	100% bedridden. Completely disabled. Cannot carry on any	20	Very sick, hospitalization indicated. Death not imminent.	
4	self-care. Totally confined to bed or chair.	10	Moribund, fatal processes progressing rapidly.	
5	Dead.	0	Dead.	

APPENDIX B: CLL RESPONSE DEFINITION (HALLEK ET AL. 2018)

Complete Remission (CR):

CR requires all of the following criteria:

- Peripheral blood lymphocytes (evaluated by blood and differential count) below $4x10^9/L$ ($4000/\mu L$).
- Absence of significant lymphadenopathy by physical examination and CT scan. Lymph nodes should be < 1.5cm in longest diameter.
- No hepatomegaly or splenomegaly by physical examination. A CT scan of the abdomen should be performed at response assessment and should show no evidence for lymphadenopathy and splenomegaly. A measurement of 13cm in cranio-caudal length has been accepted as a consensus definition for splenomegaly.
- Absence of disease-related constitutional symptoms.
- Blood counts above the following values: Neutrophils more than 1.5 x 10⁹/L (1,500/μL) without need for exogenous growth factors, Platelets more than 100 x 10⁹/L (100,000/μL) without need for exogenous growth factors, Hemoglobin more than 11.0 g/dL without red blood cell transfusion or need for exogenous erythropoietin.
- Bone marrow aspirate and biopsy must be at least normocellular for age, without evidence for typical CLL lymphocytes by morphological criteria. This evaluation is not based on a flow cytometry-based MRD assessment. When performing marrow biopsies in clinical trials, lymphoid nodules can be found that may reflect residual disease. These nodules may be recorded as "nodular PR". Immunohistochemistry may be performed to define whether the nodules are comprised primarily of T cells, of B cells other than CLL cells or of CLL cells. If nodules are not composed of CLL cells, a CR can be documented provided all other criteria are met.

Complete Remission with incomplete marrow recovery (CRi):

Some patients fulfill all the criteria for a CR, but have a persistent anemia, thrombocytopenia or neutropenia apparently unrelated to CLL, but related to drug toxicity. These patients should be considered as a different category of remission, CR with incomplete marrow recovery (CRi). For the definition of this category, CRi, the marrow evaluation should be performed with scrutiny and not show any clonal disease infiltrate.

Minimal Residual Disease

Patients who achieve CR or CRi will be assessed for minimal residual disease (MRD). Such patients who have fewer than 0.01% (10⁻⁴) CLL cell percentage of leukocytes in the bone marrow, as assessed by four-color flow cytometry, will be considered to be MRD-negative.

Partial Remission

To define a partial remission, at least one parameter of group A and one parameter of group B need to improve, if previously abnormal (see Table 13 and sections 5.2.1-5). If only one parameter of both groups A and B was abnormal prior to therapy, only 1 needs to improve.

Constitutional symptoms persisting for more than 1 month should be recorded.

Group A

a. Decrease in the number of blood lymphocytes by 50% or more from the value before therapy.

- b. Reduction in lymphadenopathy compared to baseline (by cross-sectional imaging scans in clinical trials or by palpation in general practice) as defined by:
 - A decrease in lymph node size by 50% or more in the sum of the products of the same enlarged lymph nodes selected at baseline as assessed by imaging (up to 6 lymph nodes if possible) AND the sum of the longest diameters of the same enlarged lymph nodes selected at baseline as assessed by physical exam.
 - No increase in any lymph node, and no new enlarged lymph node (diameter ≥ 1.5 cm). For small lymph nodes (longest diameter < 1.5 cm), an increase of < 25% is not considered to be significant.
- c. A regression of \geq 50% of the extent of enlargement of the spleen below the costal margin defined by palpation, or normalization in size. When assessed by CT, scan spleen size must have regressed by \geq 50% in length beyond normal. A persistence of splenomegaly post therapy may have limited influence on outcome in CLL.
- d. A regression of $\geq 50\%$ of the extent of enlargement of the liver below the costal margin defined by palpation, or normalization in size. Given the impact of numerous medical conditions, liver size by physical examination or by CT scan is not a reliable measure of hepatic involvement by CLL and should only be counted if hepatomegaly is clearly attributable to lymphoid involvement.

Group B

- a. Blood count should show one of the following:
 - Platelet count $> 100 \times 10^9 / L (100 000 / \mu L)$ or 50% improvement over baseline.
 - Hemoglobin >110 g/L (11.0 g/dL), or 50% improvement over baseline without requiring red blood cell transfusions or exogenous erythropoietin.

Progressive Disease

Progressive disease during or after therapy is characterized by at least one of the following, when compared to nadir values:

- Lymphadenopathy. Progression of lymphadenopathy is often discovered by physical examination and should be recorded. For CT scans used to confirm progression or relapse of lymphadenopathy, progression is defined as:
 - Appearance of any new lesion such as enlarged lymph nodes (≥ 1.5 cm), splenomegaly, hepatomegaly or other organ infiltrates. Transient increases of lymph node size during treatment with novel inhibitors may occur and should not be counted as PD.
 - An increase by 50% or more in greatest determined diameter of any previous site (≥ 1.5 cm).
- An increase in the spleen size by 50% or more or the de novo appearance of splenomegaly. In the setting of splenomegaly, the splenic length must increase by $\geq 50\%$

of the extent of its prior increase beyond baseline (e.g., a 15-cm spleen must increase to \geq 16 cm). If no prior splenomegaly was observed at baseline or if splenomegaly has resolved with treatment, the spleen must increase by at least 2 cm from baseline.

- An increase in the liver size of ≥ 50% of the extent enlargement of the liver below the costal margin defined by palpation, or the de novo appearance of hepatomegaly. Given the impact of numerous medical conditions, liver size by physical examination or by CT scan is not a reliable measure of hepatic involvement by CLL and should only be counted if hepatomegaly is clearly attributable to lymphoid involvement.
- An increase in the number of blood lymphocytes by 50% or more with at least 5.000 B lymphocytes per μL. (*Note:* because of the well-described lymphocyte redistribution phenomenon, any increase in lymphocyte count during acalabrutinib monotherapy or any increase during combination therapy in the setting of improvement of lymph nodes or cytopenias will not be considered disease progression)
- Transformation to a more aggressive histology (eg, Richter syndrome). This diagnosis must be established by lymph node biopsy.
- Occurrence of cytopenia (neutropenia, anemia, or thrombocytopenia) due to CLL.
 - o During therapy, cytopenias cannot be used to define disease progression.
 - O After therapy, the progression of any cytopenia (unrelated to autoimmune cytopenia), as documented by a decrease of Hb levels by more than 2 g/dL or to less than 10 g/dL, or by a decrease of platelet counts by ≥50% or to less than 100 000/μL, which occurs at least 3 months after treatment, defines disease progression, if the marrow biopsy is consistent with the cytopenia due to increased marrow infiltration of clonal CLL cells and is not considered a treatment related toxicity.

Stable Disease

Patients who have not achieved a CR or a PR, and who have not exhibited progressive disease, will be considered to have stable disease.

Treatment failure

Responses that should be considered clinically beneficial include CR and PR; all others (eg, stable disease, non-response, progressive disease, or death from any cause) should be rated as a treatment failure.

Time to Progression, progression-free survival, and overall survival

"Progression-free survival" (PFS) is defined as the interval between the first treatment day to the first sign of disease progression or death from any cause. Subjects without progression are censored at date of last disease evaluation. "Event-free survival" (EFS) is defined as the interval between the first treatment day to the first sign of disease progression or start of a new treatment or withdrawal from the trial due to toxicity or death (whichever occurs first). "Overall survival" (OS) is defined as the interval between the first treatment day to death. Living subjects are censored at date last known alive. "Time to next treatment" is defined as interval between the first treatment day until the patient starts an alternative therapy for progressive CLL.

Table 13: Response definition after treatment for CLL patients

GROUP	PARAMETER	CR	PR	PD	SD
Α	Lymph nodes	None ≥ 1,5 cm	Decrease ≥ 50% (from baseline) 1)	Increase ≥ 50% from baseline or from response	Change of - 49% to +49%
	Liver and/or spleen size*	Spleen size < 13 cm; liver size normal	Decrease ≥ 50% (from baseline)	Increase ≥ 50% from baseline or from response	Change of - 49% to +49%
	Constitutional symptoms	None	Any	Any	Any
	Circulating lymphocyte count	Normal	Decrease ≥ 50% from baseline	Increase ≥ 50% over baseline	Change of - 49% to +49%
В	Platelet count	≥ 100.000/µ1	≥ 100.000/µl or increase ≥ 50% over baseline	Decrease of ≥ 50% from baseline secondary to CLL	Change of - 49 to +49%
	Hemoglobin	≥ 11,0 g/dl (untransfused and without erythropoietin)	≥ 11 g/dl or increase ≥ 50% over baseline	Decrease of ≥ 2 g/dl from baseline secondary to CLL	Increase < 11,0 g/dl or < 50% over baseline, or decrease < 2 g/dl
	Marrow	Normocellular, no CLL cells, no B- lymphoid nodules.	Presence of CLL cells, or of B- lymphoid nodules, or not done	Increase of CLL cells by ≥ 50% on successive biopsies	No change in marrow infiltrate

 Sum of the products of 6 or less lymph nodes (as evaluated by CT scans and physical exam in clinical trials, or by physical exam in general practice).

CR, complete remission: all of the criteria have to be met; PR, partial remission: for a PR at least 1 of the parameters of group A and 1 parameter of group B need to improve if previously abnormal. If only one parameter of both groups A and B is abnormal prior to therapy, only 1 needs to improve. PD, progressive disease: at least one of the above criteria of group A or group B has to be met; SD, stable disease: all of the above criteria have to be met. Constitutional symptoms alone do not define PD.

^{*}Spleen size is considered normal if < 13 cm. There is not firmly established, international consensus of the size of a normal liver; therefore, liver size should be evaluated by imaging and manual palpation in clinical trials and be recorded according to the definition used in a study protocol.

